Most of the data on SD in cancer patients come from patients with breast cancer, gynecologic neoplasms, and prostate cancer, most of whom receive hormonal cancer treatments and cytotoxic chemotherapy, and have often undergone mutilating cancer surgeries.

There are limited prospective studies carried out with heterogeneous collection instruments, which does not allow obtaining adequate and complete information on the real situation of the problem.

As a source of local data, there is a study to characterize sexual dysfunction in a cohort of cancer survivor patients derived from the European CLARIFY H2020 project (Cancer Long Survivor Artificial Intelligence Follow-Up) that we carried out at the Puerta de Hierro University Hospital from May 2020 to May 2022.

A total of 383 patients were included, distributed according to diagnosis in breast cancer 68.1% (261), lung cancer 26.3% (101) and lymphomas 5.48% (21).

Globally, 69% of men vs. 31% of women reported being sexually active and 76% of women vs. 24% of men had general sexual dissatisfaction.

In our study, the largest sample of patients was women with breast cancer (261), which corresponds to the highest overall frequency reported in the literature of this type of neoplasm.

In relation to the stage, patients with early breast cancer treated and followed up receiving hormonal therapy showed a greater tendency to suffer moderate disorders of the phases of sexual response, while patients with a diagnosis time greater than 5 years showed a tendency to not present alterations. Statistically significant associations were confirmed in patients with metastatic breast cancer to present severe disorders of the phases of sexual response.

Regarding the specific characteristics of patients with lung cancer, which represented a smaller sample size (101), 66.3% (67) were men, the median age was 64 and 61 years in men and women respectively. 45% of women and 41% of men reported being sexually active. The absolute frequency of overall sexual dissatisfaction was 8.8% in men vs. 2.8 in women.

Men showed a tendency to develop severe alterations in the phases of sexual response. On the other hand, a statistically significant association was evidenced for severe sexual response disorders in women. Of these, 35.2% received chemotherapy, 26.4% immunotherapy and 20.5% targeted therapies.

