When looking for similar information in the literature, we found previous research in women with lung cancer that supports that 95% of these patients score below the 50th percentile when rating their sexual function and a 2022 study, in which 64% had metastatic disease, and almost half were receiving targeted therapy, finding that 77% reported moderate to severe sexual dysfunction.

Our data obtained in patients with lung cancer, despite representing a small sample size, suggest that SD is an alteration that is significantly affecting the quality of life of this population.

In addition, they suggest that there is a potential role for new cancer treatments such as targeted therapy and immune checkpoint inhibitors in the development of DS, for which there is limited information

Justification

Given the increase in lung cancer survivors and the therapeutic options different from those historically described as associated with DS, added to the fact that the patient profile has changed in recent years, with the male gender remaining the most affected, but with a significant increase in diagnosis in women and younger and non-smoking patients; it is important to characterize SD in this population and determine its severity as well as the associated risk factors and the role of new antineoplastic therapies.

This knowledge will make it possible to propose strategies for approaching and monitoring cancer that help improve the quality of life of these patients during and after cancer treatments.

A study is planned to be carried out with a larger number of patients with lung cancer, including the population of Spain and Latin American countries to obtain a sample of more diverse and heterogeneous characteristics, with clinical, cultural and sociodemographic differences. This will allow us to obtain better and greater data and consequently to define the clinical and treatment factors significantly associated with SD in these individuals and to obtain a more complete view of the reality of the problem.

The results of this research will make it possible to carry out interventions specifically aimed at this population and modify the oncological follow-up guidelines currently in force. Likewise, the information collected will serve as a basis for generating new protocols for a multidisciplinary approach including the participation of psychology and specialists in urology, gynecology and psychiatry.

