Additionally, the knowledge obtained will allow to generate education about SD to the entire treating medical team and patients to overcome the barriers that prevent adequately addressing this condition.

7. General Objective

To identify and describe the type, frequency, and severity of SD in patients with lung cancer and to generate targeted clinical approach and oncological follow-up strategies based on specific findings in this population.

8. Secondary Objectives

- Describe the clinical, cultural, and sociodemographic characteristics of the study population.
- To characterize differences in sexual dysfunction in patients with lung cancer according to age, sociodemographic characteristics, region of residence, and type of cancer treatment.
- Identify risk factors for the development and severity of sexual dysfunction.
- To promote education and awareness among the health team on the identification and characteristics of sexual dysfunction in patients with lung cancer.
- To collect information to generate recommendations for the multidisciplinary approach and management of sexual dysfunction during oncological follow-up applicable to current oncology practice.
- To propose education strategies on the management of sexual dysfunction in patients with lung cancer aimed at patients and their families.
- To generate a collaborative network of Ibero-American research.

9. Methods and procedures envisaged, including statistical and other analytical tests

The recruitment will be carried out from July 2023 and will be carried out until December 2023, the analysis of the information will be carried out from January to March 2024.

Clinical and demographic variables (Annex 1) will be collected by the treating oncologists and recorded in an electronic data collection notebook designed for this study, which will be accessed through a personal username and password.

Data anonymization will be ensured for all patients. To this end, they will identify themselves with a numerical code in order to respect the confidentiality of personal data. The patient's initials and medical record number will be separated from the rest of the data and will not be included in the study database.

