Measurements of sexual function will be performed through an electronic survey that will be sent to patients who agree to participate in the study and sign the informed consent. This electronic survey will be hosted on an exclusive study platform, which the patient will enter through a user corresponding to the anonymization numerical code and a personal password assigned after signing the informed consent.

The survey will consist of single-choice questions based on two validated questionnaires to explore and diagnose sexual dysfunction in women (FSM) and men (FSH) separately, which have been evaluated and translated into Spanish by a local research group in the Valencian Community and are available for use in the primary care setting in Spain. These instruments were selected because of the possibility of self-administration, their history of efficacy in assessing complete sexual function in the general population, and their low level of complexity. Through this instrument, criteria of the phases of sexual response according to DSM V (FSH) and DSM IV (FSM) will be evaluated, as well as a descriptive parameter of sexual activity. (Appendices 2 and 3)

The information entered by patients will only be visible by the principal investigator, who will have a personal username and password to access the data.

10. Statistical analysis

A descriptive analysis of the variables will be carried out; for the characteristics a univariate analysis. The qualitative variables will be determined with absolute and relative frequencies and the quantitative variables by measures of central tendency and dispersion, with mean and standard deviation for those with normal and median distribution and interquartile range for those with non-normal distribution. Subsequently, an inferential analysis will be performed, with chi2 distribution to evaluate the correlations between the different variables and the main outcomes in the measurement of sexual function.

Possible trends in association between variables and outcomes will be evaluated and the main trends described will be carried out through a multivariate analysis.

Logistic regression analyses will be performed to determine risk factors

Statistical analyses will be carried out using the SPSS Statistics 20 or R program.

11. Full project overview in understandable language

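### Section 10 tests associations with a plain chi-square that makes no allowance for recruiting centre; a comparison by region of residence is over-precise if region largely follows centre and outcomes correlate within centres

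*Combined protocol and SAP*

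**What the plan says.** Section 8 (Secondary Objectives) plans to characterise differences in sexual dysfunction "according to age, sociodemographic characteristics, region of residence, and type of cancer treatment". The Justification in Section 6 describes a larger study "including the population of Spain and Latin American countries to obtain a sample of more diverse and heterogeneous characteristics". Section 12.1 refers to participating institutions in the plural, and Section 9 has treating oncologists collecting the clinical data. Patients therefore enter through centres.

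Section 10 gives one bivariate test: "an inferential analysis will be performed, with chi2 distribution to evaluate the correlations between the different variables" and the main outcomes. It adds that "the main trends described will be carried out through a multivariate analysis" and that "Logistic regression analyses will be performed to determine risk factors". No covariates are listed for either step. Centre, country, clustering, stratification, random effects and robust variance are not mentioned in Section 10 or elsewhere in the supplied text. Region is not defined there either, and Annex 1, which lists the variables, was not supplied.

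**The concern.** A chi-square test assumes independent patients. Patients treated at one hospital share case mix, treatment practice, local culture and the way they were invited to the survey, so their answers may be correlated. For a factor that varies among patients within a centre this does little harm. For a factor that is constant within a centre, such as Spain versus Latin America, the effective unit of comparison is nearer the centre than the patient, and the chi-square understates the standard error.

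At stake is one named secondary comparison: ordinary centre-to-centre variation could be read as a regional difference.

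**Working it through.** The plan states no alpha, sample size or power, so it has no figure to reproduce. The check asks how far a nominal two-sided 5% chi-square on 1 df drifts when region has two levels and is fixed by centre.

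**Inputs from the documents.** Section 6 describes a cohort "that we carried out at the Puerta de Hierro University Hospital from May 2020 to May 2022", with 101 lung cancer patients, 67 of them men and so 34 women. Section 9 gives a six-month recruitment window, July to December 2023. At the same pace one centre would recruit 101/24 × 6 = 25.25 patients. This is a rough guide from a single hospital.

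**Assumptions, not from the documents.** Alpha 0.05; equal centre sizes of m = 5, 10 or 25; ICC 0.01 or 0.05.

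**Formulas.** Design effect DE = 1 + (m − 1) × ICC. Actual error = 2 × [1 − Φ(1.96/√DE)]. The correct standard error is √DE times the chi-square one.

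| m per centre | ICC | DE | √DE | Actual error |
|---|---|---|---|---|
| 5 | 0.01 | 1.04 | 1.02 | 5.5% |
| 5 | 0.05 | 1.20 | 1.10 | 7.4% |
| 10 | 0.01 | 1.09 | 1.04 | 6.0% |
| 10 | 0.05 | 1.45 | 1.20 | 10.4% |
| 25 | 0.01 | 1.24 | 1.11 | 7.8% |
| 25 | 0.05 | 2.20 | 1.48 | 18.6% |

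**By sex.** Section 9 measures women and men with separate questionnaires. Splitting 25.25 by the Section 6 ratio gives 25.25 × 34/101 = 8.5 women and 25.25 × 67/101 = 16.75, about 17, men.
- Women, m = 8.5: DE = 1.075 and 1.375, error 5.9% and 9.5%.
- Men, m = 17: DE = 1.16 and 1.80, error 6.9% and 14.4%.

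**Check by simulation.** Beta-binomial outcomes with no true region effect agree with the formula. For example, with 20 centres of 20 patients, ICC 0.05 and outcome rate 0.77, the simulated error is 15.9% against 16.0% from the formula. With the factor balanced inside each centre (rate 0.50, ICC 0.01 to 0.10) it is 3.5% to 5.5%, so there is no material inflation.

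**Does a centre-aware method repair it?** A logistic GEE was simulated with exchangeable correlation, bias-corrected robust standard errors and a t reference on (centres − 2) df.
- Centres split 50:50 or 30:70 between two regions, 6 to 60 centres: error 2.5% to 5.6%.
- 10 centres split 2:8: 7.0% to 8.9%.
- 20 centres split 3:17: 8.3% to 9.2%.
- 20 centres split 2:18: 12.9% to 13.9%, against 8.8% for the plain chi-square at ICC 0.01.

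The correction works when both regions have a reasonable number of centres and fails when one region has two or three.

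**The case against.** The strongest reply is that the text does not commit to the faulty analysis. Section 10 speaks of variables in general and never names region. The objective is to characterise differences, and the multivariate and logistic steps could include centre or country. This stands in part: centre is unstated in the models, not excluded. But the chi-square is the only bivariate test given and region is a planned comparison variable. Adding country to a logistic model would not by itself correct the region standard error for clustering by centre.

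Second, region is undefined. If it means something that varies within a centre, such as urban versus rural residence, the problem shrinks. This stands, and it is why the point is conditional.

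Third, 25 per centre in one pooled outcome may be too high. This also stands. Analysis by sex lowers the error, as shown above. If only sexually active patients were evaluable (an assumption, using 41% of men and 45% of women from Section 6), it would fall to about 5.7% to 8.5% in men and 5.3% to 6.7% in women.

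A reader might infer more than the documents support:
- That the study promises a declared regional difference, because it aims "to define the clinical and treatment factors significantly associated with SD in these individuals". Those words concern clinical and treatment factors, not region.
- That treatment comparisons are confounded by country. That would arise only if country is left out of the models, and the covariates are simply not listed.
- That centre is not recorded. Without Annex 1 this cannot be judged.

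**Conclusion.** The point holds in conditional form. If region of residence is largely fixed by centre, and outcomes correlate within centres, the chi-square in Section 10 is over-precise for region. Both conditions are plausible where patients are recruited by their treating oncologists in different countries, but neither is established by the documents.

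The size runs from negligible (about 5.5% with 5 patients per centre and ICC 0.01) to serious (18.6% with 25 and ICC 0.05). These are scenarios under assumed centre sizes and ICCs, and the top figure should not be read as the expected error. Comparisons by age or sex should change little. The general objective, which is to describe type, frequency and severity, does not depend on this test. The change is worth making because it is cheap and protects a named secondary comparison.

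**What to change.** 1. Define region of residence, and confirm that centre and country codes stay in the analysis file with the patient's numerical code.
2. For region, replace the plain chi-square with an analysis that allows for clustering by centre: a logistic model with a random centre intercept, or a logistic GEE with small-sample-corrected standard errors and a t reference.
3. Fix the method and degrees of freedom before outcomes are analysed, once the number of centres per region is known. No single default suits every layout. The (centres − 2) rule assumes two regions. The random-intercept likelihood-ratio test had simulated error of 4.3% to 9.2% with 10 centres and 4.1% to 6.7% with 40 or 60.
4. Do not use fixed centre effects for a region contrast that is fixed by centre, because the contrast is then not estimable.
5. If a region has only two or three centres, report the region difference descriptively. If there is one centre per country, say that country and centre cannot be separated.

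The cost is SAP wording and slightly more analysis in R, which Section 10 already names. No new patient data are needed if centre and country are already recorded. The downside is wider intervals and less power for region: in the scenarios above, standard errors are 1.02 to 1.48 times the naive ones.

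### Risk factors for the severity of sexual dysfunction are an objective, and severity is described in ordered grades, but section 10 names no ordinal method

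*Combined protocol and SAP*

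**What the plan says.** Severity appears twice among the objectives. The general objective (section 7) is "To identify and describe the type, frequency, and severity of SD in patients with lung cancer". A secondary objective (section 8) makes it an inferential question: "Identify risk factors for the development and severity of sexual dysfunction".

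Where the document describes severity, it uses grades. In the pilot (section 6, theoretical framework), one group of breast cancer patients "showed a greater tendency to suffer moderate disorders of the phases of sexual response", others tended to have no alterations, and in lung cancer "Men showed a tendency to develop severe alterations in the phases of sexual response". An outside study of women with lung cancer is cited as "finding that 77% reported moderate to severe sexual dysfunction".

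Section 10 gives the analysis. For the bivariate step, "an inferential analysis will be performed, with chi2 distribution to evaluate the correlations between the different variables and the main outcomes". Trends in association are then to be examined and taken into a multivariate analysis that is not specified. Finally, "Logistic regression analyses will be performed to determine risk factors". Section 10 does not state the form of the chi-square test, the form of the logistic regression, its dependent variable, or any cut-point for severity. Section 9 refers to Appendices 2 and 3 for the two questionnaires (FSM for women, FSH for men); those appendices are not in the text available for this review.

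**The concern.** An analysis of risk factors for severity asks whether patients with a given factor tend to fall in higher grades. A Pearson chi-square does not ask that: it gives the same value however the grades are arranged, and it spreads a directional effect over several degrees of freedom. Binary logistic regression needs the grades collapsed to two classes, so the answer depends on where the line is drawn. If the line is chosen after the data are seen, that choice can decide which factors are declared significant.

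At stake is efficiency and reproducibility for one stated objective. The loss would be felt most in small subgroups. Women and men complete different questionnaires, so severity is naturally analysed by sex, and the pilot had only 101 − 67 = 34 women with lung cancer.

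**Working it through.** The plan gives no sample size, significance level, power or effect size, so it has no figure of its own to reproduce. What follows is illustrative.

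**Inputs from the document:** graded severity, with three grades visible in the pilot text (no alterations, moderate, severe); 77% moderate to severe in one outside study; 101 lung cancer patients in the pilot.

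**Assumed:** two near-equal groups; two-sided 5% level; a common cumulative odds ratio (OR) of 1.5 or 2; total N of 101, 200 or 400; three equal grades, four equal grades, or four skewed grades (8/15/37/40%, so 37 + 40 = 77% in the upper two).

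**Step 1: the effect assumed.** An OR of 2 halves the odds of lying at or below each grade. With three equal grades, the cumulative odds 0.5 and 2 become 0.25 and 1, giving cumulative proportions 0.20 and 0.50. The comparison is 33/33/33% against 20/30/50%.

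**Step 2: sample-size ratio.** Find the noncentrality λ at which a chi-square test with d degrees of freedom has 80% power: P(χ²_d(λ) > χ²_d,0.95) = 0.80. This gives λ = 7.85 for d = 1, 9.63 for d = 2 and 10.90 for d = 3. Noncentrality grows in proportion to N. If the ordered 1-df test captures the whole shift, the ratios of N are:
- three grades (2 df): 9.63 / 7.85 = 1.23
- four grades (3 df): 10.90 / 7.85 = 1.39

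Where the ordered test needs 200 patients, the unordered test needs about 246 or 278.

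**Step 3: simulated power** (20,000 replicates, OR 2), unordered chi-square versus Wilcoxon:

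| Grades | N = 101 | N = 200 | N = 400 |
|---|---|---|---|
| Three equal | 36.4% vs 45.5% | 65.8% vs 75.1% | 92.6% vs 96.1% |
| Four equal | 33.1% vs 48.4% | 61.0% vs 77.3% | 91.2% vs 97.0% |
| Four skewed | 29.8% vs 45.0% | 56.0% vs 73.3% | 88.4% vs 95.6% |

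Across these and the OR 1.5 scenarios the loss runs from 3.5 points (three grades, OR 2, N = 400: 96.1 − 92.6) to 17.4 points (four equal grades, OR 1.5, N = 400: 62.0 − 44.6).

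**Step 4: collapsing to two classes.** With four skewed grades, OR 2 and N = 400, the three possible cuts give 35.2%, 75.3% and 93.3% power, against 95.6% for the ordered test. With three equal grades and N = 200, the two cuts give 57.9% and 68.3%, against 75.1%. A well-placed cut can lose little and a poor one a great deal.

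**Step 5: validity.** With no effect (OR 1), every test rejected between 4.4% and 5.8% of the time. The issue is power and choice of cut, not false positives from the tests themselves.

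**The case against.** A reader might infer that the plan prescribes an unordered test. It does not say so. Trend tests are also referred to a chi-square distribution, logistic regression includes the proportional-odds model, and section 10 mentions trends. This stands as a limit on the point: the unordered form is the ordinary reading of the words, not a stated choice. It does not remove the point. No trend test is named, and the account of the pilot in section 6 uses tendency for suggestive associations, as distinct from statistically significant ones. If an ordinal analysis is intended, section 10 still has to say so.

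A reader might also infer that the plan has no scoring for severity. That is not supported: the scoring may be in Appendices 2 and 3, which were not available. Scoring would define the grades; the choice of test and model for them would still belong in section 10.

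The 1.39 ratio should not be the headline. It needs four grades, and no mild grade appears in the document; the three grades that do appear give 1.23. Both ratios assume a consistent shift and a two-group factor. If the effect is not monotone, the ordered test need not do better.

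Finally, region of residence and type of cancer treatment, both named in section 8, are nominal. A linear-by-linear test does not suit them, so one trend test for every factor would be the wrong remedy. With numbers like the pilot's 34 women, a proportional-odds model with many covariates would be fragile.

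**Conclusion.** The point holds as an analysis choice that should be changed and written down. Severity risk factors are an objective, the document describes severity in ordered grades, and section 10 names only methods whose usual forms ignore the order or require a cut. It is not a demonstrated wrong test, and it does not make the results invalid.

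For a consistent shift between two groups, the cost is about 23% more patients with three grades or 39% with four, or 3.5 to 17.4 points of power in the scenarios tried. A poorly placed binary cut can cost much more. These sizes rest on assumed group sizes, effect sizes and numbers of grades; none can be fixed from the plan.

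**What to change.** In section 10, treat severity as an ordered outcome, separately for FSM and FSH, and state:

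- **Bivariate tests:** Wilcoxon for two-group factors; Kruskal-Wallis for nominal factors with more groups (region, treatment type); a linear-by-linear trend test only where the factor is itself ordered.
- **Risk-factor model for severity:** proportional-odds logistic regression, with a check of its assumption, limited to few covariates where numbers are small.
- **Presence versus absence of SD:** binary logistic regression, with the cut for each questionnaire fixed before the data are seen.

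The cost is wording only. No new data are needed, and both SPSS and R fit these models. The downside is an assumption to check, and no gain if the effect is not monotone across grades.

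### In the bivariate step, section 10 names only chi-square, so age can enter that step only in undefined bands, and the plan does not say that age stays continuous in the later logistic regression

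*Combined protocol and SAP*

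**What the plan says.** Section 8 (Secondary Objectives) sets as its second objective "To characterize differences in sexual dysfunction in patients with lung cancer according to age, sociodemographic characteristics, region of residence, and type of cancer treatment". Its third is separate: "Identify risk factors for the development and severity of sexual dysfunction".

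Section 10 treats the two kinds of variable differently when it describes them. Qualitative variables get frequencies, and it summarises "the quantitative variables by measures of central tendency and dispersion". For inference it then names one bivariate method for all variables, "with chi2 distribution to evaluate the correlations between the different variables and the main outcomes in the measurement of sexual function". No t-test, rank test or univariable regression is named for a quantitative variable.

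Two further sentences follow. One reads "Possible trends in association between variables and outcomes will be evaluated and the main trends described will be carried out through a multivariate analysis". The other reads "Logistic regression analyses will be performed to determine risk factors". Neither says how age will be coded. Age bands are not defined anywhere in the available text. The list of clinical and demographic variables (Annex 1) is cited in section 9 but is not part of that text, so it cannot be seen whether age is recorded as a number or in categories.

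**The concern.** A chi-square test of association compares counts across categories. To put age into it, someone must choose cut points. Three things are then at stake for the age part of the second objective.

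- **Information.** Patients within a band are treated as having the same age. The test also ignores the order of the bands when there are three or more. Both reduce power against a steady age gradient.
- **Choice after seeing data.** With no bands fixed in advance, the result depends on cut points that can be chosen late, and the size of the loss varies with that choice.
- **Carry-over.** The sentence on trends can be read as sending only the main bivariate findings on to the multivariate analysis, although it does not say so. If chi-square results did decide what goes forward, an age effect missed in the first step might never reach the model. If the same bands were reused as an adjustment term, some confounding by age would remain in the treatment comparison. The documents state neither.

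**Working it through.** The documents give no sample size, significance level, power or age effect, so there is no figure of the plan's own to reproduce. The check asks what chi-square on banded age would lose relative to a test on continuous age.

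**Inputs from the documents**

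- Eligible age is 18 to 70 years (section 12.2).
- In the earlier institutional cohort, which included 101 patients with lung cancer, "the median age was 64 and 61 years in men and women respectively" (section 6).
- A cited study of women with lung cancer found 77% with moderate to severe dysfunction (section 6). This is used as one outcome rate.

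**Assumptions**

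- Two-sided 5% level.
- Log-odds of dysfunction linear in age.
- Age normal with mean 65 and SD 10, truncated to 18 to 70. This gives median 61.0, mean 59.9 and SD 7.0.
- Effect size set so that the continuous test has about 80% power.
- For the simulation: N of 101, 200 or 400, and a second outcome rate of 50%.

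**Step 1. Noncentrality of the continuous-age test (1 df) at 80% power**

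λ = (1.960 + 0.842)² = 7.85.

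**Step 2. Noncentrality after banding**

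λ_b = 7.85 × R², where R² is the share of the variance of age that lies between bands.

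**Step 3. Power and sample size**

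Power = P(noncentral chi-square with k − 1 df and noncentrality λ_b exceeds the 5% critical value), for k bands. The multiplier on N needed to recover 80% is (noncentrality required at k − 1 df) ÷ λ_b. The required values are 7.85, 9.63, 10.90 and 11.94 for 1, 2, 3 and 4 df.

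| Age coding in chi-square | df | R² | λ_b | Power | N multiplier |
|---|---|---|---|---|---|
| Median split | 1 | 0.639 | 5.02 | 61.0% | 1.56 |
| Single cut at 60 | 1 | 0.662 | 5.20 | 62.5% | 1.51 |
| Single cut at 65 | 1 | 0.448 | 3.52 | 46.6% | 2.23 |
| Tertiles | 2 | 0.797 | 6.26 | 60.3% | 1.54 |
| Under 50, 50–59, 60 and over | 2 | 0.823 | 6.46 | 61.8% | 1.49 |
| Quartiles | 3 | 0.864 | 6.78 | 57.5% | 1.61 |
| Quintiles | 4 | 0.900 | 7.06 | 54.5% | 1.69 |

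Worked line for the median split: 7.85 × 0.639 = 5.02; √5.02 − 1.960 = 0.28; Φ(0.28) = 0.61; 7.85 ÷ 5.02 = 1.56.

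Finer bands keep more of the age variance but spend more degrees of freedom, so adding bands does not recover the power.

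**Step 4. Simulation check** (3,000 runs for each of the six combinations of N and outcome rate)

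- Continuous age, score test as in univariable logistic regression: 74 to 83%.
- Chi-square on two to four bands, apart from the cut at 65: 52 to 68%.
- Chi-square with a cut at 65: 38 to 47%.
- Linear trend test on quartiles: 68 to 75%.
- Mann–Whitney test on age: 71 to 79%.

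The ordering matches the analytic result. Methods that keep the order or the value of age recover most or all of the loss.

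**The case against.** The strongest reply is that section 10 does not stop at chi-square. It goes on to trends, a multivariate analysis and logistic regression, and logistic regression takes continuous age directly. A reader might infer that chi-square is the only association analysis planned, or that the study as a whole must lose power to detect an age gradient. The documents do not support either. Banding is forced only in the bivariate step, and if age enters the regression as continuous the loss does not occur there. This part of the objection stands and limits the point.

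It does not remove the point. The coding of age in the regression is not stated. The regression is assigned to risk factors, which is the wording of the third objective, and not expressly to differences by age. The trends sentence names no test and does not say that age is kept ordered or continuous. The bivariate results are also likely to be reported in their own right.

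A reader might also infer that the loss arises because most patients fall in a narrow age range. The documents give medians from an earlier cohort and an upper limit of 70, but no measure of spread. Spread is in any case not what drives the loss: rescaling age leaves R² for a median split, tertiles or quartiles unchanged, and a narrow range weakens the continuous test too.

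Two further limits are fair. The linear effect assumed here favours the continuous test, and a non-monotone relation could change the comparison. Age differences are also one part of one secondary objective, while the general objective is descriptive.

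**Conclusion.** The point holds for the bivariate step. There, the only named test requires age and any other quantitative variable to be banded, with no bands defined in the available text. Where a continuous-age test would have about 80% power, the chi-square test has about 54 to 62% for usual bandings and about 47% for a cut at 65. Recovering 80% would take about 1.5 to 1.7 times the patients, or 2.2 times for the cut at 65.

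These sizes are conditional on the assumed significance level, effect size, age distribution and linearity. They describe one step of the analysis and are not a property of the whole plan. Whether the loss extends to the logistic regression cannot be settled from the documents, because the coding of age and the rule for selecting variables are not stated. The change is worth making because it improves the stated method at almost no cost, but it concerns a secondary objective.

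**What to change.** In section 10:

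1. Limit the chi-square test to qualitative variables.
2. For age and every other quantitative variable, test the association with sexual dysfunction with the variable kept continuous, for example by univariable logistic regression.
3. Keep these variables continuous in the planned multivariable logistic models, and state that the models also serve the age-differences objective. Add a check of the shape of the age effect, such as a restricted cubic spline with few knots, if the sample allows.
4. Use age bands only in descriptive tables, with the bands fixed before the data are seen.

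This costs one or two sentences and needs no new data, provided that age is recorded as a number; Annex 1 should be checked for this. Logistic regression is already planned in the named software. The downside is a little more analysis, and a few extra degrees of freedom if a spline is used.
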